9 SAFETY AND ADVERSE EVENTS

9.1 Definitions

The definitions for adverse event, adverse device effect, serious adverse event, serious adverse device effect, and unanticipated adverse device effect are provided below (ISO 14155:2011, 21 CFR 812.3(s)).

- **Adverse Event (AE):** an adverse event is any untoward medical occurrence in a subject which need not be related to the device under investigation.
- **Adverse Device Effect (ADE):** an adverse device effect is any untoward or unintended response to a medical device which may result from insufficiencies in the instructions for use or deployment of the device, or from use error.
- **Serious Adverse Event (SAE):** a serious adverse event is an adverse event that results in death, inpatient hospitalization, severe or permanent disability, a life threatening illness or injury, fetal distress, fetal death, a congenital abnormality, a birth defect, or medical or surgical intervention to prevent permanent impairment to body or structure.
- **Serious Adverse Device Effect (SADE):** a serious adverse device effect is an adverse device effect that results in death, inpatient hospitalization, severe or permanent disability or is life threatening.
- **Unanticipated Adverse Device Effect (UADE):** any serious adverse effect on health or safety or any life threatening problem or death cause by or associated with, a device, if the effect, problem, or death was not previously identified in nature, severity or degree of incidence in the investigational plan, or application (including a supplementary plan or application) or any other unanticipated serious problem associated with a device that related to the rights, safety or welfare of subjects. Refer to Risk and Benefit section 5 for details on anticipated adverse device effects.

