5 RISKS AND BENEFITS

The major risks to the patient are related to the surgical procedure (bleeding, infection, pain, etc.). Participation in this protocol places the patient at minimal if any additional risk. There is theoretical extremely small risk of damage to the subject's fingers from the device including potential temporary redness or skin irritation or discomfort associated with exposure to the sensor.

There is no intervention and no alteration to the patient's surgical procedure. Patient will receive standard patient care. All additional measurements will be done through non-invasive sensors. None of the data recorded through these sensors will be used to make decisions regarding the patient.

Noninvasive measurement with Masimo Corporation Radical 7 pulse oximetry: The risk is minimal since the measurement is noninvasive and uses optical technology similar to conventional pulse oximetry.

Sensor risks: As with all optical sensors, the device has the risk of thermal burn. The design includes safeguards, and this risk is believed to be low. All patient-contact materials, including the adhesive used in the design of the Masimo Rainbow sensors, have been subjected to biocompatibility tests per ISO 10993-1 and results demonstrate that the materials are non-toxic, non-irritating, and non-sensitizing. The sensors have been subjected to performance, mechanical, and electrical testing and results demonstrate that the sensors meet the requirements for safety and effectiveness for the intended use of the product. Pressure damage may occur to the tissue if the sensor is placed too tightly.

Volume expansion risks: Risks of volume expansion with [REDACTED] can include fluid accumulation in the lungs or tissue, decreased oxygen saturation, and edema.

There will be no direct benefits to the enrolled patients. Future benefits to patients might include a reduction in invasive procedures due to the ability to trend moment-by-moment physiological parameters.

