9.3 Adverse Event Reporting

The PI must promptly report the following adverse events to the Sponsor through the CRF and Adverse Event Report Form, and follow their IRB policy for safety event reporting:

- All Adverse Events, both anticipated and unanticipated and both serious and non-serious, after the first Masimo sensor is placed and up to the last Masimo sensor is removed
- All Unanticipated Adverse Device Effects after the first Masimo sensor is placed and up to the last Masimo sensor is removed

SAEs and UADEs must be reported to the Sponsor within 48 hours. All other Adverse Events should be reported to the Sponsor within 5 business days.

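### Section 9.1 omits prolonged hospitalization from the seriousness criteria, and its SADE definition drops a criterion that the SAE definition contains

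*Combined protocol and SAP*

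**What the plan says.** Section 9.1 defines an adverse event (AE) broadly: "an adverse event is any untoward medical occurrence in a subject which need not be related to the device under investigation". It becomes an SAE by a list of outcomes: "a serious adverse event is an adverse event that results in death, inpatient hospitalization, severe or permanent disability, a life threatening illness or injury", followed by fetal and congenital outcomes and "medical or surgical intervention to prevent permanent impairment to body or structure".

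For device effects, section 9.1 says "an adverse device effect is any untoward or unintended response to a medical device", and the serious form has a shorter list: "a serious adverse device effect is an adverse device effect that results in death, inpatient hospitalization, severe or permanent disability or is life threatening". The unanticipated adverse device effect (UADE) has its own wording, beginning "any serious adverse effect on health or safety or any life threatening problem or death", and is limited to effects not already identified in the plan.

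Section 9.3 requires every AE, serious or not, to be reported if it occurs between placement of the first sensor and removal of the last. SAEs and UADEs go to the sponsor within 48 hours. "All other Adverse Events should be reported to the Sponsor within 5 business days". SADEs have no deadline of their own.

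Section 5 names the harms at issue. For the volume expansion these are fluid in the lungs or tissue, lower oxygen saturation and edema. For the sensor they include thermal burn, and "Pressure damage may occur to the tissue if the sensor is placed too tightly".

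**The concern.** Study exposure takes place in the operating room. A subject already admitted for the operation can hardly be hospitalized as a result of an event there; the usual consequence is a longer stay, which neither list mentions. Read strictly, the hospitalization criterion catches nothing in such a subject. Read loosely, it could catch every event, because the subject is in hospital anyway. Either way, the grade depends on the reader and not on the event.

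The second problem is an unexplained mismatch. The SAE list counts treatment needed to avert lasting damage; the SADE list does not. Burns and pressure injuries, the device harms that section 5 itself names, are the kind of injury for which that criterion matters.

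At stake are the reporting clock for one class of event, and the completeness of the SADE category, whose documentation the monitor verifies under section 11.5.

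**Working it through.** The plan gives no figure on this point, so there is none to reproduce. The check sets the two lists in section 9.1 side by side, runs two example events through sections 9.1 and 9.3, and converts the deadlines to calendar time.

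| Outcome | In SAE list | In SADE list |
|---|---|---|
| Death | yes | yes |
| Inpatient hospitalization | yes | yes |
| Longer stay for a subject already admitted | no | no |
| Severe or permanent disability | yes | yes |
| Life threatening | yes | yes |
| Intervention to avert permanent impairment | yes | no |
| Fetal or congenital outcome | yes | no |

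**Event A: fluid in the lungs after the volume expansion, during the sensor window, in an admitted subject.** It adds days in hospital but is not life threatening, not disabling and not treated to avert permanent impairment.
- It is an AE, and it meets no outcome in the SAE list.
- The fluid is not the device, so the device-effect categories, and therefore the SADE gap, play no part.
- Section 9.3 places it among all other AEs: 5 business days.

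**Event B: a sensor burn or pressure injury treated to avert permanent impairment, with no other serious outcome.**
- It is an AE, because that definition does not exclude device-related events, and it is an adverse device effect.
- It meets the SAE list through the intervention criterion, so it is due in 48 hours.
- It meets nothing in the SADE list, so it is not a SADE.
- Whether it is a UADE is open. The UADE definition points to section 5 for anticipated effects, where burn and pressure damage are named. Section 9.2, however, anticipates only mild allergic reactions and discomfort, redness or irritation at the sensor site, so the severity could be argued to be unanticipated.
- The delay from the SADE omission is 48 h − 48 h = 0 h.

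**Calendar time for Event A.** Assume that the count starts on the day after the event and that there are no holidays.
- Event on a Sunday: the fifth business day is Friday, 5 calendar days later (5 × 24 = 120 h).
- Event on a Saturday: also Friday, 6 calendar days later (144 h).
- Event on any weekday: one weekend intervenes, so 5 + 2 = 7 calendar days (168 h).
- Difference from the 48-hour clock: 120 − 48 = 72 h at the least and 168 − 48 = 120 h at the most, that is 3 to 5 days. Elective surgery on a weekday gives the upper end.

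**The case against.** The strongest reply is that the consequences are narrow.

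- *Inpatient status is not stated.* Section 4.2 requires only elective surgery with general anesthesia and mechanical ventilation, and section 4.5 has consent signed on the morning of surgery. For a same-day patient, an unplanned admission would still meet the criterion. This stands as a limit. Section 1.1 describes cardiac surgery, and section 7 has radial and pulmonary arterial catheters inserted, so admission is likely; but it is an inference.
- *Most serious harm is still caught.* Events that are fatal, life threatening, disabling or treated to avert permanent impairment remain SAEs, whether caused by fluid or by the sensor. This stands: the first gap concerns only events whose sole serious consequence is a longer stay.
- *Nothing in the window goes unreported.* Section 9.3 collects all AEs and asks for prompt reporting. This stands: the gap affects grade and deadline, not whether the event is recorded. Fluid harm that first appears after sensor removal falls outside the reporting window. That is a separate limit, which new definitions would not change.
- *The delay is between ceilings.* A site may report sooner, and section 9.3 does not say when the clock starts. A longer stay is often recognized only days after onset, so adding the criterion does not guarantee a report within 48 hours of the event. This stands: 3 to 5 days is the gap between deadlines, not a forecast of actual delay.
- *The SADE gap changes only a label.* The monitor checks SAEs and SADEs together, and Event B is seen as an SAE. This is right about timing and visibility, but it does not explain why the serious device category should leave out a device injury that the plan itself grades as serious.

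**Conclusion.** Both gaps are in the text of section 9.1 and should be closed. For admitted subjects, an event serious only because it prolongs the stay is graded non-serious, and its deadline moves from 48 hours to 5 business days, about 3 to 5 days later on the counting assumptions shown. Separately, a sensor injury treated to avert permanent impairment is left out of the SADE count while being an SAE and an adverse device effect; its reporting time is unchanged. The first conclusion rests on subjects being inpatients, which is likely but not stated for all. The second rests on the wording alone. No sample size, endpoint or efficacy result is affected.

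A reader might infer three stronger things, none of which the documents support.

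- *That serious sensor harm is reported late.* It is not: Event B keeps the 48-hour clock through the SAE definition.
- *That a later report means a further subject is exposed.* The plan has no rule that halts enrolment on a single report. The safety termination rule in section 12.4 is tied to UADEs and allows up to 15 working days after the sponsor's first notice, and section 13 makes the on-site principal investigator evaluate all AEs whatever the sponsor's clock.
- *That the trial's safety conclusion will be too favourable.* Section 2.1 has no safety objective, section 8 has no safety analysis or SADE tabulation, and the 510(k) mention in section 10.6 concerns record retention.

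**What to change.** Make these edits in section 9.1:

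1. In the SAE definition, replace the hospitalization criterion with *inpatient hospitalization or prolongation of existing hospitalization*.
2. State that the planned surgical admission is not itself an event. This removes the reading under which every event in an admitted subject is serious.
3. Define a SADE as an adverse device effect that meets any SAE criterion. This carries over both the prolongation and the intervention criteria and keeps the two lists aligned in future amendments.

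Leave the 48-hour clock in section 9.3 as it is. The cost is two edited definitions and matching fields on the case report form and adverse event form, with a few more events likely to be reported within 48 hours.

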9.2 Anticipated Adverse Events

- Mild allergic reaction to sensor material and adhesives.
- Discomfort, redness or skin irritation at site of sensor placement.

9.3 Adverse Event Reporting

The PI must promptly report the following adverse events to the Sponsor through the CRF and Adverse Event Report Form, and follow their IRB policy for safety event reporting:

- All Adverse Events, both anticipated and unanticipated and both serious and non-serious, after the first Masimo sensor is placed and up to the last Masimo sensor is removed
- All Unanticipated Adverse Device Effects after the first Masimo sensor is placed and up to the last Masimo sensor is removed

SAEs and UADEs must be reported to the Sponsor within 48 hours. All other Adverse Events should be reported to the Sponsor within 5 business days.

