1.3 Risk/Benefits

Benefits: There is no specific benefit to the individual subjects for participation in this research protocol.

Sensor risks: As with all optical sensors, the investigational device has the risk of thermal burn. Pulse CO-oximeter noninvasive measurement uses wavelengths in the red and near infrared range like a conventional pulse oximeter used in routine clinical practice for over 15 years. The additional LEDs from Rainbow sensors have been tested and meet the Exempt classification for photo-biological safety of light sources.

All patient-contact materials, including the adhesive used in the design of the Masimo Rainbow sensors, have been subjected to biocompatibility tests per ISO 10993-1 and results demonstrate that the materials are non-toxic, non-irritating, and non-sensitizing. The sensors have been subjected to performance, mechanical, and electrical testing and results demonstrate that the sensors meet the requirements for safety and effectiveness for the intended use of the product.

No other physical, financial, social or psychological risks are anticipated to be associated with participation in this study. Precautions taken to safeguard protected personal health information are described in **section 4.4** on recruitment. The risks associated with the anesthetic and surgical procedure are not discussed in this protocol.

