7 STUDY PROCEDURES

- Patients are assigned to be ventilated in a volume controlled mode with a tidal volume of either 6 or 8 $\text{ml} \cdot \text{kg}^{-1}$ of ideal body weight (Devine formula) at a frequency [REDACTED]. Positive end-expiratory pressure is to be set [REDACTED] according to the attending physician.
- Anesthesia is induced as per standard of care. Radial and pulmonary arterial catheters inserted as per standard of care.
- All required sensors are placed as per the corresponding instructions for use for the various measurements
- All patients are to be studied [REDACTED] with no changes in anaesthetic protocol and no volume expansion. Unless clinically contraindicated, patients will receive an intravenous volume expansion consisting of [REDACTED] given over [REDACTED].
- Baseline set of haemodynamic measurements (stroke volume and or cardiac output) are to be performed prior to the intravenous volume expansion.
- A repeat set of hemodynamic measurements are to be performed [REDACTED] after volume expansion.

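### Sponsor reporting of adverse events stops at sensor removal, so fluid-related or skin events that appear later need not be reported; the risk statements also contradict each other

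*Combined protocol and SAP*

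**What the plan says.** Section 9.3 asks the investigator to report to the sponsor every adverse event, serious or not and expected or not, but within a period defined by the sensor: "after the first Masimo sensor is placed and up to the last Masimo sensor is removed". UADEs have the same limits. The section also tells the investigator to "follow their IRB policy for safety event reporting"; the content of that policy is not given.

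Section 7 sets two study procedures besides the sensor. First, "Patients are assigned to be ventilated in a volume controlled mode with a tidal volume of either 6 or 8" ml/kg of ideal body weight. Second, unless clinically contraindicated, patients receive an intravenous volume expansion. Section 5 says that the risks of the expansion "can include fluid accumulation in the lungs or tissue, decreased oxygen saturation, and edema", and for the sensor it names thermal burn and pressure damage.

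Section 9.2 lists two anticipated events: a mild allergic reaction to the sensor, and "Discomfort, redness or skin irritation at site of sensor placement". Section 9.1 adds: "Refer to Risk and Benefit section 5 for details on anticipated adverse device effects".

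Three general statements stand beside this. Section 2.1 calls the study non-interventional. Section 5 says: "There is no intervention and no alteration to the patient's surgical procedure". Section 1.3, after describing the sensor, says: "No other physical, financial, social or psychological risks are anticipated to be associated with participation in this study".

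**The concern.** A window that opens and closes with the sensor suits a study whose only added exposure is the sensor. Here the protocol also gives fluid, and the only systemic risks it attributes to a study procedure are those of the fluid. Section 9.3 does not tie reporting to that procedure. If lung or tissue fluid, or a fall in saturation, shows itself after the sensor is off, section 9.3 does not require the sponsor to be told.

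The same holds for the sensor site. Section 1.2 has the sensor on a finger and shielded from outside light, and section 4.2 requires general anesthesia. A patient cannot report discomfort while the sensor is on, and a burn or pressure mark may be seen only once it is off.

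At stake is the completeness of the safety information that the sponsor and the investigator use to judge whether the study is safe to continue (section 13). The accuracy results for RPVi are not at stake.

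**Working it through.** The point rests on no power, alpha or event-rate figure, so there is nothing to recompute. The check sets the sections side by side.

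**1. What the window covers.** The adverse event definition in section 9.1 does not require a relation to the device. With section 9.3, any event of any cause is reportable while a sensor is on. The second null hypothesis in section 2.1 concerns the change in RPVi after the bolus, so a sensor must be on before the expansion and at the repeat measurement. Fluid effects that appear in that period are inside the window.

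**2. What it leaves out.** Both bullets of section 9.3 end at sensor removal. The visible text gives no removal time and no safety follow-up after the repeat measurement, and section 4.1 limits participation to one visit. Section 9.3 also does not say whether an event is placed in the window by its onset or by its detection. If by onset, a burn first seen after removal would count, but no later inspection is required that would find it. The 48-hour sentence in section 9.3 sets a deadline for serious events and UADEs; it does not state a longer window.

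**3. Whether late events can be recovered.** Section 10.1 has the site destroy the list linking case numbers to patients as soon as extraction is complete. After that, an event missed by the window may no longer be linkable to a subject.

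**4. The two risk lists.**

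| Risk | Section 5 | Section 9.2 |
|---|---|---|
| Redness, irritation, discomfort | yes | yes |
| Mild allergic reaction | no | yes |
| Thermal burn | yes | no |
| Pressure damage | yes | no |
| Lung or tissue fluid | yes | no |
| Decreased saturation | yes | no |
| Edema | yes | no |

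Both of the 2 events in section 9.2 are sensor effects, and 0 of the 3 volume-expansion risks in section 5 appear there. The pointer in section 9.1 does not repair this for fluid effects, because it concerns device effects only.

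**5. The general statements.** Section 1.3 anticipates no further physical risk, while section 5 lists three for the expansion. Sections 2.1 and 5 describe a study without intervention, while section 7 assigns the tidal volume and gives the expansion. These contradictions need no assumption.

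**The case against.** The case for leaving section 9.3 alone is substantial. Everything that happens during the bolus and the repeat measurement is already reportable. Section 10.4 has the case report form record any adverse event, without a sensor window. Section 13 makes the investigator evaluate all adverse events and device effects, again without a window, and local IRB policy may reach further. Section 8 plans no safety endpoint, so no safety estimate is biased. There is no group without the expansion, so later edema or desaturation in a surgical patient could not readily be attributed to it.

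Most of this stands, and it limits the point. It does not close the gap. Sections 10.4 and 13 set no period of observation, the IRB policy is not described, and section 9.3 is the only section that states a window. Weak attribution is a reason to interpret late events with care, not a reason to leave them unreported.

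Three stronger readings are tempting, and the documents do not support them.

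- *A reader might infer that the mismatched lists decide whether a sensor burn triggers the 48-hour report or the termination clock in section 12.4.* They do not. Section 9.1 defines a UADE against the whole investigational plan and points to section 5, where burn and pressure damage are named. A UADE must be serious, and section 9.3 gives all serious events 48 hours, anticipated or not. Section 12.4 applies only once the sponsor finds an unreasonable risk.
- *A reader might infer that harms of the assigned tidal volume go unreported.* Section 1.1 states no significant risk or benefit of either volume in patients without significant pulmonary disease, and section 4.3 excludes chronic lung disease. The bullet order in section 7 does not show a period of assigned ventilation before sensor placement, since it also lists ventilation before induction.
- *A reader might want a count of missed events.* The documents give neither a rate of fluid-related events nor the share that appears late, so any count would be invented.

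**Conclusion.** The concern holds in a limited form. Section 9.3 requires no sponsor report of events that first appear after the last sensor is removed, although section 5 lists risks of the protocol's own volume expansion that may appear then, and although sensor skin injury may first be seen then. The size of this gap cannot be judged: removal time is not in the visible text, and the fluid and the timing of the repeat measurement are blacked out in section 7. The conclusion assumes that no follow-up rule stands in the text between sections 2.1 and 4, which was not available here.

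The mismatch between sections 5 and 9.2, and the conflict of sections 1.3, 2.1 and 5 with section 7, are plain on the text and rest on no assumption. The mismatch makes the anticipated label inconsistent, but it changes no duty to report an adverse event, since section 9.3 covers anticipated and unanticipated events alike. The point concerns safety ascertainment and the description of risk. It is worth an amendment and does not touch the RPVi analysis.

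**What to change.** 1. In section 9.3, keep the start at first sensor placement and move the end to a fixed time after the volume expansion, for example recovery-room discharge. State whether the window is judged by onset or by detection. Take respiratory, fluid-related and sensor-site events up to that time from the routine chart, before the linking list in section 10.1 is destroyed.
2. Align section 9.2 with section 5, so that one list covers the sensor effects (including burn and pressure damage) and the volume-expansion risks.
3. Reconcile the statements in sections 1.3, 2.1 and 5 about risk and absence of intervention with the assigned tidal volume and the expansion in section 7.

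The cost is a protocol amendment and a short chart check per subject, for up to 150 subjects, with no added visit or procedure and no change to care. The downside is that some surgical events will be recorded that cannot be attributed to the bolus; they should be reported descriptively, without a causal claim.
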